Clinical Trial Protocol

NCT Number: NCT07043829

Protocol ID: PCSAEPF29-2021

Official Title: Effect of Consuming a Cimarrón Bean Extrudate Solution on Platelet Function and Postprandial Biochemical Parameters.

Sponsor: University of Talca, Chile.

Principal Investigator: PhD. [name]

Ethics Approval: Folio 29-2021 (Approved)

Version Date: June 19th, 2025

1. Background

The common bean (*Phaseolus vulgaris*), a legume with high nutritional value, has been shown to have beneficial effects on cardiovascular health. Its bioactive components, including proteins, polyphenols, and fiber, contribute to the modulation of platelet activity. Evidence from previous studies indicates that regular bean consumption may reduce inflammatory markers, oxidative stress, and overall cardiovascular risk, positioning it as a key functional food for the prevention and management of chronic diseases. Incorporating beans into the regular diet could represent a practical strategy to improve cardiovascular health and promote healthy eating habits in the general population. The primary objective of this trial is to obtain preliminary evidence on the acute capacity of the extrudate to reduce thrombotic activity under controlled conditions, minimizing potential confounding factors that could happen when using a delivery vehicle.

2. Objectives

General Objective

To analyze the acute effect of consuming a *Phaseolus vulgaris* L. var. Cimarrón extrudate solution on platelet function, postprandial blood glucose, and total plasma polyphenol levels.

Specific Objectives

1. To evaluate the effect of consuming SPVCE (Solution *Phaseolus vulgaris* L var. Cimarrón extrudate) on platelet function, assessed by PFA and platelet reactivity.
2. To determine the change in postprandial blood glucose after consuming SPVCE.

3. To quantify the effect of consuming SPVCE in postprandial total plasma polyphenol levels.

3. Study Design

Model Description: A single-arm, open-label, acute, non-randomized interventional study in which all participants consumed a single dose of a functional solution containing 10 grams of *Phaseolus vulgaris* L var. Cimarrón extrudate dissolved in water. No placebo or comparator group is included. Outcomes are measured before and after the intervention within the same participants to assess acute changes in platelet function, postprandial glycemia, and total plasma polyphenol levels.

4. Participants

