Records will be kept confidential by the responsible researcher. Participant names or identifiers will not be used. Blood samples will be labeled with codes and will not be linked to personal data. Identity and health information will not be disclosed and will remain confidential. Study approved by the University of Talca Scientific Ethic Committee (Folio 29-2021).

Statistical Analysis Plan (SAP)

NCT Number: NCT07043829

Protocol ID: PCSAEPF29-2021

Official Title: Effect of Consuming a Cimarrón Bean Extrudate Solution on Platelet Function and Postprandial Biochemical Parameters.

Sponsor: University of Talca, Chile.

Principal Investigator: PhD. [name]

Ethics Approval: Folio 29-2021 (Approved)

Version Date: June 19th, 2025

1. Introduction: This Statistical Analysis Plan (SAP) outlines the methods and procedures for analyzing the data from the clinical trial investigating the acute effects of a Cimarrón Bean Extrudate solution on platelet function and postprandial biochemical parameters.

2. Analysis Populations

- **Per-protocol (pp) population:** Includes all participants who complete the 8-hour observation period and have valid measurements for the outcomes of interest without major protocol deviations (e.g., incomplete fasting, incomplete product ingestion, prohibited medication use). Sensitivity analyses will be conducted in the PP population to verify robustness.
- **Available Case Analysis:** An analysis based on all available data pairs for each outcome; participants with missing paired data will be excluded from that specific analysis.

3. Software: All statistical analyses will be performed using *GraphPad Prism version 10*.

4. General Analysis Design

- The planned sample size is **n = 30**.
- Measurements were obtained at baseline (0 h, pre-ingestion) and at **2 h** and **6 h** after consumption of the extrudate solution.

- Continuous variables will be expressed as mean \pm standard deviation (SD) when approximately normally distributed, or median [interquartile range, IQR] when non-normal.
- Categorical variables will be presented as frequency and percentage. For each time point, the mean/median and change from baseline will be reported.

5. Assessment of Normality and Homogeneity

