Normality of data will be evaluated using the Shapiro–Wilk test, and homogeneity of variances will be assessed using Levene’s test where applicable. All statistical tests will be two-sided with the significance level set at $p < 0.05$.

6. Primary Endpoint

- Platelet Function (Flow Cytometry – Dose–Response Analysis): For each activation marker (P-selectin and fibrinogen) and agonist (ADP, TRAP-6, CRP), dose–response curves will be generated using non-linear regression to determine EC₅₀, maximum response, minimum response, and response span per participant. Comparisons of these curve-derived parameters between baseline (0 h) and 6 h post-ingestion will be performed.

The analysis will proceed as follows: For curve-derived parameters (EC₅₀, maximum, minimum, and response span), normality of paired differences between baseline and 6 h will be assessed using the Shapiro–Wilk test. If data are normally distributed, paired t-tests will be used for comparisons; if non-normal, Wilcoxon signed-rank tests will be applied. For the dose–response curves themselves, a two-way ANOVA will be performed to evaluate the effects of treatment (baseline vs. 6 h) and agonist concentration. If assumptions for parametric analysis are met, Sidak’s multiple comparisons post hoc test will be applied. If assumptions are not met and the analysis is non-parametric, a corresponding non-parametric alternative to two-way ANOVA will be used, followed by Dunn’s multiple comparisons post hoc test. Data will be presented as mean \pm SD for normally distributed data and median [IQR] for non-normal data

7. Secondary Endpoints

1. **Platelet Function (Closure Time – PFA-200):** Paired differences between baseline (0 h) and 6 h will be analyzed after testing for normality with the

Shapiro–Wilk test. Normally distributed data will be compared using a paired t-test, and non-normal data using the Wilcoxon signed-rank test.

2. **Baseline and Postprandial Glucose:** Differences between 0 h and 2 h will be analyzed using the same normality testing and paired statistical approach (t-test or Wilcoxon).
3. **Plasma Total Polyphenols Concentration:** Repeated measures at 0 h, 2 h, and 6 h will be analyzed using one-way repeated measures ANOVA if normality assumptions are met, followed by an appropriate post hoc test (e.g., Tukey's or Sidak's) for parametric data. If non-parametric, the Friedman test will be used, followed by Dunn's multiple comparisons post hoc.

8. Missing Data Handling

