- The primary analysis will be conducted as an available-case analysis: only complete pairs of baseline and post-dose measurements will be included for paired comparisons, excluding any missing pairs. The number of pairs included will be reported for each analysis.
- If missing data in the primary variable is $\leq 5\%$, only available-case analysis will be performed without imputation.
- If missing data exceeds 5% or is suspected not to be missing completely at random, sensitivity analyses will be conducted using appropriate methods such as:
 - Linear mixed models for repeated measures (assuming Missing At Random), or
 - Multiple imputation (e.g., predictive mean matching) and comparison with available-case results.
- Participants lacking estimable parameters for a specific variable will be excluded from analyses involving that parameter; actual sample sizes will be reported accordingly.

9. Multiple Comparisons Correction

No formal correction for multiple comparisons will be applied. The primary endpoint analyses are limited to a small set of predefined parameters (EC_{50} , max, min, span) for key activation markers and agonists. Secondary endpoint analyses will be considered exploratory. Given the focused nature of the primary analyses and the sample size, results will be interpreted with caution regarding multiplicity. Where applicable, post hoc tests controlling type I error (e.g., Sidak's or Dunn's tests) will be used following ANOVA or non-parametric analyses.

10. Safety and Adverse Events

Gastrointestinal symptoms and any adverse events will be summarized as frequencies and percentages. Where applicable, events will be reported by post-ingestion time point.

11. Sample Size and Power

The planned sample size of **n = 30** is based on feasibility and prior experience in acute postprandial studies. With n = 30 for paired comparisons, the study has approximately **80% power** to detect a medium effect size (Cohen's $d \approx 0.5$) at $\alpha = 0.05$ (paired t-test).

12. Presentation of Results

Results will be presented in tables and figures. Tables will include descriptive statistics per time point, changes from baseline with 95% confidence intervals, and adjusted p-values where applicable. Figures will present time–response profiles, dose–response curves, and bar plots of key comparisons.

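### SAP 7.3 leaves the polyphenol comparisons open and names the all-pairs Tukey test first, although only the two comparisons with 0 h are needed

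*Combined protocol and SAP*

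**What the plan says.** Protocol section 2, specific objective 3, reads "To quantify the effect of consuming SPVCE in postprandial total plasma polyphenol levels". Protocol section 3 describes one arm, no comparator, and measurement before and after the dose in the same people. SAP section 4 states "For each time point, the mean/median and change from baseline will be reported", and SAP section 12 lists "changes from baseline with 95% confidence intervals" among the table contents.

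SAP section 7, item 3 covers the three polyphenol time points. The parametric branch is a one-way repeated measures ANOVA, "followed by an appropriate post hoc test (e.g., Tukey's or Sidak's) for parametric data". The non-parametric branch is Friedman, then Dunn's test. Neither branch says which pairs will be compared. In items 1 and 2 of the same section, closure time and glucose each have a single stated comparison with 0 h.

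SAP section 9 treats the secondary endpoints as exploratory and applies no formal correction beyond the post hoc tests.

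**The concern.** In a single-arm study the effect of consumption can only be estimated as a post-dose value minus the 0 h value. That gives two contrasts. Three time points make three pairs, and no objective or reporting item asks for a test of the third, 2 h vs 6 h. Tukey's test adjusts for all three pairs by construction. Sidak's and Dunn's adjust for as many pairs as the analyst enters, and the SAP does not give that number.

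Two things are at stake. Power for objective 3 is lower than it needs to be if the family has three members. And because both the test and the family are open, a borderline change at 2 h or 6 h could be significant or not depending on a choice made after the data are seen.

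**Working it through.** **Inputs.** Two-sided alpha of 0.05 (SAP section 5: "All statistical tests will be two-sided with the significance level set at" 0.05). Thirty complete participants (SAP section 11: "With n = 30 for paired comparisons, the study has approximately" 80% power). Standardized change d = 0.5, in units of the SD of the paired difference (SAP section 11). That value is generic; the documents give no effect or SD for polyphenols, so its use here is an assumption.

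**The SAP's own figure first.** For one unadjusted paired test, d√n = 0.5 × √30 = 2.739. The normal approximation gives Φ(2.739 − 1.960) = Φ(0.779) = 78.2%, in line with "approximately 80% power". The exact noncentral t with 29 df gives 75.4%. Both apply to a single unadjusted comparison, so neither is the power of an adjusted polyphenol contrast.

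**Critical values on |t|.**
- Tukey: upper 5% point of the studentized range for 3 means, divided by √2.
- Sidak over three pairs: t quantile at per-comparison alpha 1 − 0.95^(1/3) = 0.0170.
- Sidak over two pairs: the same at 1 − 0.95^(1/2) = 0.0253.
- Dunnett: two contrasts sharing the 0 h mean, correlation 0.5.

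Power for one baseline contrast is the noncentral t probability beyond ±c with noncentrality 2.739. It is shown for pooled repeated-measures error (58 df) and for a separate error per contrast (29 df).

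| Method | c, 58 df | Power, 58 df | c, 29 df | Power, 29 df |
|---|---|---|---|---|
| Tukey, 3 pairs | 2.41 | 63.1% | 2.47 | 60.9% |
| Sidak, 3 pairs | 2.46 | 61.2% | 2.53 | 58.5% |
| Sidak, 2 pairs | 2.30 | 67.1% | 2.36 | 64.9% |
| Dunnett, 2 pairs | 2.27 | 68.1% | 2.32 | 66.1% |

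**Loss against Dunnett at d = 0.5.** Tukey: 68.1 − 63.1 = 5.0 points (58 df) and 66.1 − 60.9 = 5.2 (29 df). Sidak over three: 68.1 − 61.2 = 6.9, or 7.0 before rounding, and 66.1 − 58.5 = 7.6. The range is therefore about 5 to 8 points.

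**Rank branch.** Simulated power of Dunn's test after Friedman (independent normal errors, both post-dose means shifted by 0.5) is about 44% with three comparisons and 49% with two, a loss of about 5 points.

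**Dependence on d (29 df, loss against Dunnett; Tukey first, then Sidak over three).** d = 0.4: 5.3 and 7.6 points. d = 0.6: 3.9 and 5.7. d = 0.7: 2.2 and 3.3. d = 0.8: 0.9 and 1.5.

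**Effect of an omnibus gate.** The figures so far let the post hoc test run regardless of the ANOVA. If it runs only after a significant F test, simulation (58 df, 100,000 trials) gives, for 2 h vs 0 h:
- both post-dose means shifted by 0.5: Tukey 62.7%, Dunnett 66.4%, a loss of 3.7 points; Sidak over three loses 5.4 points;
- 2 h shifted by 0.5 and 6 h by 0.25: losses of about 2 points (Tukey) and 3 points (Sidak over three).

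Gated, the loss is therefore about 2 to 5 points.

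**The case against.** The strongest reply is that the SAP commits to no all-pairs analysis. Tukey and Sidak are introduced only as examples, and section 9 mentions Sidak's and Dunn's tests but not Tukey's. Sidak's test limited to the two baseline pairs reaches 67.1% against Dunnett's 68.1%, so almost nothing would be lost. This stands. A reader might infer that every named post hoc test is all-pairs and that the 5 to 8 points are certain to be lost. The text does not support that: only Tukey is all-pairs by construction, and the loss arises only if a three-pair family is used.

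A reader might also infer that the intervals promised in SAP section 12 will be too wide. There, the adjustment is attached to the p-values, and no adjusted interval is promised. Only if intervals were matched to the tests would they widen, by 2.41/2.27 to 2.46/2.27, or about 6% to 8%.

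The size is conditional too. The value 0.5 is not a polyphenol estimate, larger effects shrink the loss, and the usual reading of a post hoc test following an ANOVA implies a gate, which also shrinks it.

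Finally, objective 3 does not use the words change from baseline, and whether levels persist from 2 h to 6 h is a fair postprandial question. But the design and SAP sections 4 and 12 point to baseline contrasts, and persistence can be shown descriptively in the planned time–response figures. What remains is an unspecified comparison set and a first-named example that fits the question poorly.

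**Conclusion.** The point holds as a low-severity improvement. The polyphenol comparison family is not prespecified. If it becomes all-pairs, each baseline contrast loses about 5 to 8 points of power against Dunnett at n = 30 and d = 0.5, about 2 to 5 points with an omnibus gate, and about 1 point at d = 0.8. These figures assume normal data, sphericity and 30 complete participants, and take d from the SAP's generic planning value.

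All-pairs adjustment brings no bias and no inflation of type I error; it is only conservative. The endpoint is secondary and exploratory, and the primary analysis is untouched.

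**What to change.** In SAP section 7, item 3, replace the open post hoc wording with: two planned comparisons against 0 h (2 h vs 0 h and 6 h vs 0 h), Dunnett-adjusted and performed whatever the result of the omnibus test. Dunnett's procedure controls the family-wise error for these two contrasts itself, so it does not need the gate. In the non-parametric branch, limit Dunn's test after Friedman to the same two pairs. Report 2 h vs 6 h descriptively.

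The cost is a change of SAP wording, with no new data, participants or procedures. The downside is that 2 h vs 6 h will have no adjusted p-value. If the sponsor wants that comparison tested, the SAP should say so and give the reason.

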- 4. Total polyphenols:** Whole blood anticoagulated with 3.2% sodium citrate processed to Thrombosis Center SOPs, centrifuged at 3000 rpm for 8 minutes at ambient temperature, obtaining platelet-poor plasma (PPP), aliquot and store at -80°C until assay if not run immediately.

Laboratories: Thrombosis Center Research, University of Talca (Platelet function assays and total polyphenols), and Clinic Laboratory Talca (glucose).

Visit schedule & sample timing

- 1. Day 0 (Treatment):** Participants arrived in fasting conditions (≥ 8 hours).
- 2. Baseline samples at T0h:** PFA-200, flow cytometry (reactivity), serum glucose, plasma total polyphenols. Administer 10 g extrudate in 500 ml water (supervised).
- 3. Post-dose samples:** T2h-serum glucose, plasma total polyphenols; T6h-PFA-200 Flow cytometry, plasma total polyphenols. Record AEs and vital signs throughout.

Discharge/follow-up: The participant has signed a request for sample storage and subsequent use of the samples in future research. Depending on the option selected (Acceptance or Rejection), the samples will be stored accordingly, labeled with the corresponding code, or discarded following the biological sample disposal protocol of the University of Talca, Chile.

8. Sample size and Statistical considerations

Planned enrollment: 30 participants

Statistical software: GraphPad Prism 10.1.1.

Statistical Plan: Paired analysis comparing pre- and post-dose measures, two-sided $p < 0.05$. More details in the SAP appendix.

9. Criteria for Withholding and Stopping

Withholding Criteria (no intervention on study day):

The investigational product will **not be administered**, and the participant's study visit will be suspended for the remainder of that scheduled 8-hour session if any of the following are present at baseline (pre-dose) or detected during the immediate pre-administration checks:

1. Acute illness or fever on the study day.
2. Fasting blood glucose ≥ 126 mg/dL or ≤ 60 mg/dL at baseline measurement.
3. Blood pressure $\geq 160/100$ mmHg at baseline assessment.

4. Self-reported moderate/severe gastrointestinal symptoms within 24 hours before the visit (e.g., vomiting, severe diarrhea, uncontrolled nausea).
5. Any acute condition deemed by the investigator to increase participant risk or compromise data integrity.

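### SAP 11 states about 80% power for n = 30 and d ≈ 0.5, but the two-sided paired t-test it names has 75.4% power, before any loss of pairs

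*Combined protocol and SAP*

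**What the plan says.** SAP section 11 explains that the sample size "is based on feasibility and prior experience in acute postprandial studies". It then adds: "With n = 30 for paired comparisons, the study has approximately 80% power to detect a medium effect size", identifying that effect as Cohen's d of about 0.5, with alpha 0.05 and a paired t-test. It gives no standard deviation, no within-person correlation and no definition of d for paired data.

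Sidedness is fixed elsewhere. SAP section 5 says "All statistical tests will be two-sided with the significance level set at" 0.05, and protocol section 8 also specifies a two-sided paired pre-post analysis.

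Protocol section 8 gives "Planned enrollment: 30 participants", the same number that the power statement uses as its number of pairs. SAP section 8 says that "only complete pairs of baseline and post-dose measurements will be included for paired comparisons, excluding any missing pairs". It also removes a participant from any analysis whose parameter cannot be estimated for that participant. Neither document gives an expected loss rate or adds participants to cover losses.

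**The concern.** SAP 11 supplies what a power check needs: n, effect size, alpha and test. With the two-sided rule from SAP 5, the result should follow by calculation, and it does not come to 80%.

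The 30 is also the most favourable number of pairs possible. The primary parameters come from non-linear fits made per participant, marker and agonist (SAP 6), and a pair exists only if both the 0 h and the 6 h fits yield the parameter. The SAP itself foresees that some will not.

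At stake is how a null result would be read. A reader relying on SAP 11 would take the chance of missing an effect of d = 0.5 to be 20%, when under the plan's own inputs it is about 25% at best.

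**Working it through.** **Inputs.** n = 30 pairs (protocol 8; SAP 4 and 11); d = 0.5, alpha = 0.05 and paired t-test (SAP 11); two-sided (SAP 5; protocol 8). Assumption: d = mean paired difference / SD of paired differences.

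**Exact power of the named test.**
- Degrees of freedom: 30 − 1 = 29. Two-sided 5% critical value: t = 2.045.
- Noncentrality: d × √n = 0.5 × √30 = 2.739.
- Power = P(|T| > 2.045), with T noncentral t (29 df, noncentrality 2.739) = **75.4%**.
- Shortfall: 80 − 75.4 = 4.6 points. Type II error: 100 − 75.4 = 24.6%, against the 20% implied.

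**Attempts to reproduce 80%.**
- Two-sided normal approximation: Φ(2.739 − 1.960) = Φ(0.779) = 78.2%. This is the closest and may be the source of the figure, but it treats the SD as known and is not the t-test named.
- One-sided t-test: 84.8%. This overshoots and contradicts the two-sided rule.
- d in units of the raw SD, with within-person correlation ρ: the paired effect is 0.5/√(2(1 − ρ)). For ρ = 0.3 it is 0.423 and power is 60.9%; for ρ = 0.5 it is 0.5 and 75.4%; for ρ = 0.7 it is 0.645 and 92.7%. Power of 80% needs ρ of about 0.55, and no ρ is stated.

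**What would give 80%** (two-sided paired t-test).
- At d = 0.5: 33 pairs give 79.5% and 34 give 80.8%, so 34 complete pairs are needed.
- At n = 30: d = 0.529, or 0.53 after rounding (80.1%).

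**Fewer evaluable pairs, d = 0.5.** The losses are assumed, because the documents state no rate.

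| Complete pairs | Assumed loss | Power |
|---|---|---|
| 30 | none | 75.4% |
| 29 | 1 pair | 73.9% |
| 28 | 2 pairs | 72.3% |
| 27 | 3 pairs (10%) | 70.6% |
| 24 | 6 pairs (20%) | 65.0% |

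**The case against.** The sentence is hedged twice, with an approximate power and an approximate d. A true d of 0.53 rounds to 0.5 and gives 80%, and a normal approximation comes within two points. SAP 11 does not define d either, so 75.4% depends on the usual paired-test reading; with a raw-SD effect and a correlation above about 0.55, power would exceed 80%. Nothing was decided from the figure, because n rests on feasibility and protocol section 1 describes the aim as preliminary evidence. SAP 8 and 12 also promise the number of pairs per analysis and 95% confidence intervals, which will show the precision achieved.

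Most of this stands as a limit on the importance of the point. It does not rescue the number. The test named is a t-test, the printed effect is 0.5, and the correlation that would be needed appears nowhere. If 0.53 was intended, the text should say so.

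Three stronger readings are tempting, and the documents do not support them:

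- **Multiplicity lowers the power.** SAP 6 defines many primary comparisons, so a reader might infer that power is far lower once corrected. SAP 9 applies no formal correction, and uncorrected multiplicity does not reduce the power of each test. A corrected figure would describe an analysis that is not planned.
- **The Wilcoxon fallback lowers it.** SAP 6 uses that test only when the paired differences are non-normal. A power figure calculated under normality does not describe that case, and the documents do not specify the non-normal distribution needed for another.
- **Losses will be substantial.** The direction is certain but the size is not. The visit is a single supervised day, and no rate of missing or non-estimable data is given.

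**Conclusion.** Wrong as written, and modest in size. For the test, sidedness, alpha, n and d that the plan gives, power is 75.4%, which is 4.6 points or four complete pairs short of the stated figure. In effect-size terms, 30 pairs have 80% power for d = 0.53, not 0.50. This rests on reading d in units of the SD of the paired differences.

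Because enrolment equals the number of pairs assumed, 75.4% is the ceiling under these inputs; every lost pair takes it lower, by an amount that the documents do not allow one to fix.

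A reader might infer that the trial is too small or that enrolment must rise to 34. That does not follow: the sample size was not derived from a power target, so the error lies in the description of the design and not in a decision based on it.

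**What to change.** Replace the power sentence in SAP 11 with wording such as:

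> n = 30 complete pairs, chosen for feasibility, gives about 75% power to detect d = 0.5, or 80% power to detect d = 0.53 (d = mean paired difference / SD of paired differences), for a single paired t-test at two-sided alpha 0.05. If 10% of pairs are not evaluable (27 pairs, an assumption), power for d = 0.5 is about 71%.

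If the sponsor has its own expectation of how many curve parameters will be estimable, that number of pairs should replace the 27 and the power be recalculated.

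The cost is one or two sentences and a slightly less favourable stated figure. Enrolment, endpoints and analyses need no change.
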